2.1.2 EXCLUSION CRITERIA

2.1.2.1 Pregnant or breast feeding females are excluded, because the toxic effects and pharmacology of pirfenidone in the fetus and newborn are unknown.

2.1.2.2 Clinically significant unrelated systemic illness (serious infections or significant cardiac, pulmonary, hepatic or other organ dysfunction), which in the judgment of the Principal or Associate Investigator would compromise the patient's ability to tolerate pirfenidone or are likely to interfere with the study procedures or results.

2.1.2.3 An investigational agent within the past 30 days.

2.1.2.4 Ongoing radiation therapy, chemotherapy, hormonal therapy directed at the tumor, immunotherapy, or biologic therapy (for example interferon).

2.1.2.5 Inability to return for follow-up visits or obtain follow-up studies required to assess toxicity and response to therapy.

2.1.2.6 Prior treatment with pirfenidone.

2.1.2.7 Evidence of an optic glioma, malignant glioma, malignant peripheral nerve sheath tumor, or other cancer requiring treatment with chemotherapy or radiation therapy.

2.2 PRE-TREATMENT EVALUATION (SEE APPENDIX 3)

Pre-treatment blood tests should be performed within 2 weeks prior to enrollment on the trial unless otherwise stated. The evaluation required prior to starting treatment is listed in table form in Appendix 3.

2.2.1 HISTORY AND PHYSICAL EXAMINATION: Complete history (including prior and concurrent therapy), physical examination including documentation of measurable disease, performance status, and signs and symptoms. Height, weight and body surface area must be recorded.

The BSA should be calculated using the formula used at the participating institution from the average of 3 repeated measurements of weight and height on the same day.

2.2.2 HEMATOLOGY: Complete blood counts, differential, platelet count.

2.2.3 CHEMISTRIES: Electrolytes (including sodium, potassium, chloride, CO₂, calcium, phosphorus and magnesium), creatinine, BUN, glucose, SGOT, alkaline phosphatase, SGPT, and bilirubin.

2.2.4 URINE OR SERUM PREGNANCY TEST: For all females of child-bearing potential (females greater than 9 years of age or those showing pubertal development). This test is to be performed within 72 hours prior to enrollment on the trial.

2.2.5 RADIOGRAPHIC EVALUATION (APPENDIX 4): MRI scan of the progressing plexiform neurofibroma(s) within 2 weeks of enrollment on study. In addition, if possible, MRI scan of all known additional, measurable plexiform neurofibroma(s) within 2 weeks of enrollment on study. The progressing plexiform neurofibroma(s) will be identified as index lesion(s), and will be studied by 3-D MRI. Should there be more than 3 progressing plexiform neurofibromas, the three most clinically relevant plexiform neurofibromas will be followed by 3-D MRI analysis. The imaging protocol outlined in Appendix 4 will be used each time MRI examinations are performed to assess the effect to pirfenidone.

2.2.6 TISSUE PROCUREMENT: Biopsy of plexiform neurofibroma, only if clinically indicated. (Tissue sent as in appendix 5).

2.2.7 QUALITY OF LIFE (QOL) ASSESSMENT: The National Institutes of Health (NIH) Impact of Pediatric Illness (IPI) Scale, which assesses the impact of disease and treatment on children's behavior, should be administered to all patients ≥ 6 and ≤ 18 years of age and their primary caregiver prior to the start of therapy. This assessment consists of an age-appropriate questionnaire and generally takes less than 30 minutes to complete. Patients between the ages of 6 and 10 years of age should be administered the IPI-Young Child form; patients between 11 and 18 years of age should be administered the IPI-Older Child/Adolescent form; the patient's primary caregiver

should receive the IPI-Parent Form. To allow for more meaningful analysis of the QOL questionnaires, a “background information sheet” will be completed by the parent one time, preferably at trial entry. This sheet includes information about education, current educational services, behavioral/psychiatric medications, visibility of NF1 tumors, and severity of NF1 symptoms. Quality of life will not be evaluated in children younger than 6 years or older than 18 years.

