1.2.10 UPDATE OF THE PEDIATRIC PHASE II TRIAL OF PIRFENIDONE

Protocol 04-C-0080 enrolled 36 patients from July 21, 2004 to July 11, 2007, and enrollment on this trial is thus complete. Pirfenidone has been well tolerated. Only 2 patients required dose reductions for dose-limiting toxicities: nausea (n=1) and grade 3 neutropenia (n=1). As of March 2008, the median number of completed treatment cycles for all patients enrolled is 10 (range 3-42 cycles). Currently nine patients remain on study: NCI POB (n=3), Children's National Medical Center, Washington, DC (n=2), Children's Memorial Hospital, Chicago, IL (n=2), Dana-Farber Cancer Institute, Boston,

MA (n=1), and Cleveland Clinic, Cleveland, OH (n=1). The median number of completed treatment cycles for these patients is 17 (9-37 cycles). The body surface area of these patients ranges from 0.66 to 1.88 m².

Initially, pirfenidone was supplied by Solanan Inc. as 200 and 400 mg capsules, and dosing for this trial was devised for identical doses three times daily on a continuous dosing schedule. The biopharmaceutical company InterMune has taken over the development of pirfenidone and will provide pirfenidone, and starting no later than May 19th, 2008, as pirfenidone shipments are requested by active sites, they will be provided by InterMune, Inc. until the trial is complete. The date for sites to begin dispensing InterMune drug supply may vary by site, depending on each site's availability of existing Solanan/Marnac supply, their procurement of IRB approval, and timing of patient re-consent. Drug supply from InterMune will be in form of 267 mg capsules. The protocol is therefore being revised in March 2008 to provide new dosing guidelines.

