2.1.1.7 Hepatic Function: Patients must have a bilirubin within normal limits and SGPT $\leq 2x$ upper limit of normal. Patients with Gilbert syndrome are excluded from the requirement of a normal bilirubin. (Gilbert syndrome is found in 3-10% of the general population, and is characterized by mild, chronic unconjugated hyperbilirubinemia in the absence of liver disease or overt hemolysis).

2.1.1.8 Renal Function: Patients must have an age-adjusted normal serum creatinine (see table below) OR a creatinine clearance ≥ 70 mL/min/1.73 m².

Age (Years)	Maximum Serum Creatinine (mg/dl)
≤ 5	0.8
$5 < \text{age} \leq 10$	1.0
$10 < \text{age} \leq 15$	1.2
> 15	1.5

2.1.1.9 Informed Consent: All patients or their legal guardians (if the patients is <18 years old) must sign an IRB approved document of informed consent (screening protocol) prior to performing studies to determine patient eligibility. After confirmation of patient eligibility all patients or their legal guardians must sign the protocol specific informed consent to document their understanding of the investigational nature and the risks of this study before any protocol related studies are performed (other than the studies which were performed to determine patient eligibility). When appropriate, pediatric patients will be included in all discussions. Age appropriate assent forms for children from 7 through 12 years, and for children from 13 through 17 years have been developed and will be signed by the pediatric patients, when appropriate, in order to obtain written assent.

2.1.1.10 Durable Power of Attorney (DPA): All patients ≥ 18 years of age will be offered the opportunity to assign DPA so that another person can make decisions about their medical care if they become incapacitated or cognitively impaired.

2.1.1.11 Patients must be able to take pirfenidone by mouth. Capsules can be opened and content mixed with food for easier consumption in small children.

2.1.1.12 Patients (both male and female) must be willing to practice birth control (including abstinence) during and for two months after treatment, if of a child-bearing age. For purposes of the protocol, all patients greater than 9 years of age or those showing pubertal development will be considered of childbearing age.

2.1.1.13 Ability and to undergo MRI and no contraindication for MRI examinations following the MRI protocol outlined in Appendix 4.

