3.4 ON STUDY EVALUATION (APPENDIX 3)

3.4.1 HISTORY AND PHYSICAL EXAMINATION: History and full physical examination, with evaluation of signs of toxicity from pirfenidone, will be repeated prior to cycles 1, 2, 3, 4, and subsequently after every 3 treatment cycles as long as the patient remains on study. Height, weight, body surface area and performance status (if

changed from baseline) must be recorded. Visible plexiform neurofibromas should be directly measured (tape measure), if possible.

3.4.2 HEMATOLOGY: Complete blood counts, differential, platelet prior to cycles 1, 2, 3, 4, 7, 10, and subsequently after every 6 treatment cycles long as the patient remains on study.

3.4.3 CHEMISTRIES: Electrolytes (including sodium, potassium, chloride, CO₂, calcium, phosphorus and magnesium), creatinine, BUN, glucose, SGOT, alkaline phosphatase, SGPT, gamma-GTP, and bilirubin prior to cycles 1, 2, 3, 4, 7, 10, and subsequently after every 6 treatment cycles long as the patient remains on study.

3.4.4 RADIOGRAPHIC EVALUATION (APPENDIX 4): Evaluate the index lesions by MRI prior to cycle 1, 4, 7, 10 and then every 6 cycles thereafter while on study. The imaging protocol outlined in Appendix 4 will be used each time MRI examinations are performed to assess progression or response to pifredone. In patients with clinical suspicion of disease progression, MRI analysis should be performed earlier using the protocol outlined in Appendix 4.

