CBC, platelets, differential*	X	X	X	X
Electrolytes, creatinine, BUN	X	X	X	X
Glucose, Ca ⁺² , Mg ⁺² , PO ₄ *	X	X	X	X
SGOT, SGPT, gamma-GTP, AP, bilirubin	X	X	X	X
Urine pregnancy test	Females			
3D-MRI of index lesions	X	Cycles 4 & 7 only	X	X
QOL assessment	X	Cycles 4 & 7 only	X	X
Review of Patient Diaries [†] :		X	after every 3 cycles	X

*Each blood draw for hematology and chemistries will require a maximum of 10 cc blood.

[†] Review of patient diaries to include compliance and toxicity monitoring.

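### Pregnancy is tested only once, before enrollment, although the protocol calls fetal effects unknown, requires birth control until two months after treatment, and sets no end to treatment

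*Combined protocol and SAP*

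**What the plan says.** **Testing.** Section 2.2.4 asks for a urine or serum test in females older than 9 years or showing pubertal development: "This test is to be performed within 72 hours prior to enrollment on the trial". The Appendix 1 checklist has space for one test date. In Appendix 3 the row "Urine pregnancy test" has a single entry, under Pretreatment.

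**On-study and off-study evaluations.** Section 3.4 repeats blood tests "prior to cycles 1, 2, 3, 4, 7, 10, and subsequently after every 6 treatment cycles" and physical examinations more often than that. It lists no pregnancy test. Section 3.7 lists urinalysis among the off-study tests, but no pregnancy test.

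**Why pregnancy matters to this protocol.** Section 2.1.2.1 excludes pregnant and breast-feeding females "because the toxic effects and pharmacology of pirfenidone in the fetus and newborn are unknown", and Section 6.1 repeats the reason. Under Section 2.1.1.12, patients of child-bearing age "must be willing to practice birth control (including abstinence) during and for two months after treatment". The same item states that "all patients greater than 9 years of age or those showing pubertal development will be considered of childbearing age".

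**Duration.** Entry is from age 3 to 21 (2.1.1.1). Treatment continues until progression or another off-study criterion (3.1.1). As of March 2008, Section 1.2.10 reports a median of 10 completed cycles and a range of 3 to 42 among all 36 patients, with nine still on study.

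**The concern.** The protocol guards against fetal exposure over one period and checks for it at one moment. The birth-control requirement covers the whole of treatment plus two months. The only check comes before enrollment and is not tied to the first dose.

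The mismatch is sharpest for a girl who enters at 9 or younger and before puberty. She has no entry test because she does not yet meet the definition. She may meet it while on drug, and no scheduled evaluation asks whether she now does. By contrast, Section 3.2.2 has the dose re-checked against body surface area at follow-up.

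The stake is patient safety. A site that follows the plan exactly does not look for an exposure that the protocol itself regards as an unknown risk. The primary endpoint is not affected.

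**Working it through.** The plan gives no figure to reproduce. The check is a comparison of the evaluation lists, with simple arithmetic on duration.

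**1. Every place where a test could appear**
- 2.2.4 (pre-treatment): one test, within 72 hours before enrollment.
- Appendix 1: one test date, at entry.
- Appendix 3: one entry, Pretreatment. The columns for cycles 2, 3, 4 and 7, for cycle 10 onward, and for Post Study are empty.
- 3.4 (on study): history and physical, hematology, chemistries, MRI, quality of life. No pregnancy test.
- 3.7 (off study): no pregnancy test.
- 3.6 (off-study criteria) and 7.3 (safety reporting): pregnancy is not named.

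These lists are intact in the text reviewed. There is also a small mismatch: 2.2.4 allows urine or serum, while Appendix 3 says urine only.

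**2. How long one test has to serve**

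Inputs: 28-day cycles without rest (3.1.1); median 10 and maximum 42 completed cycles (1.2.10). Months = cycles × 28 ÷ 30.4375.
- Median: 10 × 28 = 280 days; 280 ÷ 30.4375 = 9.2 months, or 11.2 with the two-month birth-control period.
- Maximum: 42 × 28 = 1,176 days; 1,176 ÷ 30.4375 = 38.6 months, or 40.6 with the two months.

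These durations are for all 36 patients, of unstated sex and age.

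**3. Visits that already exist through cycle 42**
- Physical examinations on treatment (3.4.1): before cycles 2, 3 and 4, then every third cycle from 7 to 40. That is 3 + 12 = 15.
- Blood tests on treatment (3.4.2, 3.4.3): before cycles 2, 3, 4, 7, 10, 16, 22, 28, 34 and 40. That is 10.

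None of these visits includes a pregnancy test.

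**4. Reaching the definition on drug**

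Treatment in years: 280 ÷ 365.25 = 0.77 at the median; 1,176 ÷ 365.25 = 3.22 at the maximum. Taking the threshold as the ninth birthday, a girl treated for the median time crosses it on drug if she enters after about 9 − 0.77 = 8.2 years. If treated for the maximum time, she crosses it if she enters after about 9 − 3.22 = 5.8 years. Reading the threshold as age 10 adds one year to each. Puberty before the threshold would bring the change forward. These ages illustrate the mechanism; the documents do not say how many such girls were enrolled.

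**The case against.** **The durations may belong to patients who never needed a test.** This stands. A reader might infer that a female of child-bearing potential went about 39 months untested. A reader might also infer that the nine patients still on study (median 17 cycles: 17 × 28 = 476 days, 15.6 months) were last tested about 16 months earlier. The documents support neither. Section 1.2.10 gives no sex or age, and the nine have body surface areas from 0.66 to 1.88 m². Males and prepubertal girls aged 9 or younger had no required test at all.

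**Reporting routes exist.** This stands in part. It would be too strong to say that only a birth defect is collected. Section 7.3.1 also counts other medically significant events as serious. Section 7.3.2 expedites events that might alter the benefit-risk assessment, Section 7.3.3 covers unanticipated problems, and the medical monitor reviews these under 7.4. Section 3.6.1 allows removal in the patient's best interest. Still, nothing names pregnancy, so reporting depends on how a site reads general wording.

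**The birth-control rule may already bind a girl who matures on study.** Section 2.1.1.12 can fairly be read that way, so it should not be said that no requirement applies to her. What is missing is a step that applies it.

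**Pregnancy could come to light anyway.** Histories and examinations are regular, and nothing bars a site from testing. A claim that it would be noticed only once clinically obvious is therefore speculation.

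**Contrary evidence and scope.** Section 1.2.6 reports no adverse embryo/fetal effect in rodents, yet the protocol still calls the human risk unknown. Objective 1.1.3 concerns toxicities in children and young adults with NF1. It is not left short of data by this gap.

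**Reach is small.** Enrollment ended in July 2007 and nine patients remained in March 2008, so a change helps only an unknown subset of them.

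**Conclusion.** The point holds as a modest safety gap. Pregnancy testing is required at entry only, no visit re-applies the child-bearing definition during open-ended treatment, and pregnancy is not named in the off-study or safety-reporting sections. This sits badly with the protocol's own statements that fetal risk is unknown and that birth control must continue until two months after treatment.

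Its size can be stated only loosely. Treatment lasted about 9 months at the median and up to about 39 months across all patients. The interval for females of child-bearing potential is not documented, and neither is any exposed pregnancy.

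The conclusion rests on reading 2.1.2.1 and 6.1 together with 2.1.1.12, since no single sentence says that exposure is a concern throughout. Consent pages and a few stretches of text, including part of Section 8.1.10, were not available. They could contain counseling or reporting instructions. The required-evaluation lists were complete.

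**What to change.** Reconcile 2.2.4, 3.4, 3.7 and Appendix 3 with 2.1.1.12 and 2.1.2.1:

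- (a) Extend the existing pregnancy-test row in Appendix 3, and the text of 3.4 and 3.7, to on-study visits already scheduled and to the off-study evaluation. The sponsor sets the frequency. State the same specimen type in 2.2.4 and Appendix 3.
- (b) At those visits, re-apply the 2.1.1.12 definition and record the result, so that a girl who meets it on study is picked up.
- (c) In 7.3.2, name pregnancy during treatment or the two-month window as an event reported to the coordinating center.

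What follows a positive test is for the investigators to specify.

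The cost is a urine test at visits that already take place, one table row and a reporting line. The protocol was already being revised in March 2008, with patient re-consent foreseen (1.2.10). The downside is repeated urine testing of young girls, for a benefit limited to the females of child-bearing age among patients still on treatment.

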2.3 PATIENT REGISTRATION

Patients must be registered by contacting [name] or [name] at the Pediatric Oncology Branch (POB) (phone number, [contact], e-mail: [contact] or [contact]). When registering a patient, information about all entry criteria (e.g., laboratory results) must be available to allow for verification of eligibility. [name] ([contact], e-mail: [contact]) or [name] ([contact], e-mail [contact]) must also be contacted to discuss the patient prior to entry on study. The POB will ship a module with the necessary materials to administer the quality of life assessment to each participating institution at the time of receipt of IRB approval of each site.

The completed Eligibility Checklist (Appendix 1) must be faxed to the POB c/o [name] or [name] ([contact]). All patients (from all institutions) will be registered with Harris Technical Services ([contact], [contact]) by the POB research nurse, and an identification number will be assigned to each patient by the POB research nurse. The POB research nurse will notify the trial sponsor [name] about registration of each patient entered on the trial by faxing eligibility checklist and trial entry document.

The POB research nurse must be notified when a participating patient is removed from the protocol. The POB research nurse will notify the trial sponsor [name] when a patient is removed from the protocol.

3.0 IMPLEMENTATION OF STUDY

3.1 STUDY DESIGN

3.1.1 OVERALL TRIAL DESIGN

This is an open label phase II trial of oral pirfenidone in pediatric and young adult patients with NF1 and inoperable, progressive plexiform neurofibromas that have the potential to cause significant morbidity. Patients will receive pirfenidone orally as capsules three times a day (“approximately” q8hours) for cycles of 28 days with no rest period between cycles (28 day treatment cycles). The investigational agent to be used in this study (pirfenidone) is not approved by the Food and Drug Administration (FDA) for commercial use; however, the FDA has permitted its use in this research study. The trial will be conducted in compliance with the GCP and applicable regulating requirements. Based upon the data from the pirfenidone phase I study in children, the dose of pirfenidone will be 500 mg/m² q8 hours (1500 mg/m²/day). Patients will remain on trial for as long as there is no disease progression and no other off study criteria have been met (Section 3.7).

This study is designed to determine the time to disease progression while on a chronic oral dose of pirfenidone (28 day cycles with no rest periods between cycles). In order to determine if pirfenidone benefits patients with NF1 and progressive plexiform neurofibromas time to disease progression on pirfenidone will be compared to time to disease progression on the placebo arm of the ongoing phase II trial of the farnesyltransferase inhibitor R115777 for children with progressive plexiform neurofibromas (Section 5.4.2).

In addition, this trial will evaluate the toxicity profile of pirfenidone in children and young adults with NF1 and progressive plexiform neurofibroma(s).

3.1.2 MONITORING TIME TO PROGRESSION AND RESPONSE

This phase II trial is designed to determine the time to tumor progression and response rate with pirfenidone in patients with NF1 and progressive plexiform neurofibromas. The primary endpoint will be time to progression. At the time of study entry the progressing plexiform neurofibroma(s) will be identified as index lesion(s), and followed for progression by 3-D MRI. Results obtained with 3-D MRI analysis will be compared to conventional 2-D MRI and 1-D MRI analysis for their ease of use, sensitivity, and reproducibility. In addition, if possible, all known additional, measurable plexiform neurofibroma(s) will be followed for progression by 3-D MRI. Results obtained with 3-D MRI analysis will be compared to conventional 2-D MRI and 1-D MRI analysis for their ease of use, sensitivity, and reproducibility. The imaging protocol outlined in Appendix 4 will be used each time MRI scans are performed to assess response to pirfenidone. MRI scans are performed prior to cycles 1, 4, 7, 10, and then after every 6 cycles while on study. All MRI studies required per protocol will be submitted to the NCI POB for assessment of response by volume measurement within 2 weeks of study acquisition. The NCI POB will notify the participating site of the volumetric measurement and response assessment. Until response assessment at the NCI POB is completed, patients will remain on treatment with pirfenidone. If a patient is removed from study because of clinical evidence of disease progression, the MRI scans should be repeated if they had not been performed within the past 6 weeks.

3.1.3 DEFINITION OF TUMOR PROGRESSION

- A $\geq 20\%$ increase in the volume (by 3D-MRI) of at least one of the index plexiform neurofibroma(s) compared to the pretreatment volume measured prior to the start of treatment.
- Appearance of new discrete dermal neurofibroma(s) does not qualify for disease progression.
- Worsening of existing symptoms or the appearance of new symptoms that persist for more than 7 days and that are felt to be definitely related to plexiform neurofibroma should be evaluated by repeating the MRI. Patients should not be classified as having progressive disease solely on the basis of new or increased symptoms without discussing the case with the protocol Principal Investigator (NCI, POB).
- Patients with other evidence of disease progression than outlined above should also be discussed with the Principal Investigator.

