The method described in Dixon and Simon (*J Clin Epidemiol* 41: 1209-1213, 1988) will be used to determine the sample size required in the present study. It will be assumed that the median time to progression of the placebo arm for the R115777 patients is 6 months, and that the eligibility criteria and distribution of potential prognostic factors for the present trial are identical to those of the R115777 trial. It is further assumed that accrual of 2.5 to 3 patients per month can be enrolled onto this trial, and that it will be of interest to identify a doubling of the median time to progression, from 6 to 12 months. A Kaplan-Meier analysis using a log-rank test is the primary method of analysis to compare the two arms. Using an intended one-sided $\alpha=0.05$, and with 50% of the 30 patients on the previous trial having progressed, at a median of 6 months, then accrual of 36 patients on the present study will provide at least 80% power to detect a doubling against the control arm from the prior trial.

Even though 30 patients have to be enrolled on the placebo arm of the ongoing phase II trial of R115777 for NF1 for a solid analysis of time to disease progression, interim analyses of time to progression will be performed while patients are still enrolled on the trial and continue on the first treatment phase. As long as the median time to disease progression on the placebo arm can be defined with reasonable precision using Kaplan-Meier analysis, a new estimate of time to disease progression can be made while the trial is still ongoing and prior to completion of the first treatment phase in all patients. The protocol may then be amended to use this estimate to adjust the sample size for the pifredone phase II trial should it be longer than anticipated.

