APPENDIX 4: PROTOCOL FOR REQUIRED PRE STUDY AND ON STUDY MRI STUDIES

Prior to starting treatment on this study all known measurable plexiform neurofibromas should be imaged with MRI to obtain a baseline. Tumor extent in patients with NF1 can be very extensive, and may not allow for all lesions to be followed using 3-D MRI.

The goal will therefore be to use 3-D MRI only to follow the progressing plexiform neurofibroma(s) (a maximum of three lesions), which will be defined as index lesion(s).

Pre-study radiographic evaluation:

- Identify and select the progressive plexiform neurofibroma(s) (a maximum of three lesions) for 3-D MRI evaluation based on prior imaging studies. Should there be more than 3 progressing plexiform neurofibromas, the three most clinically relevant plexiform neurofibromas will be followed by 3-D MRI analysis.
- Perform 3-D MRI sequences on the selected index lesions as outlined in the MRI acquisition protocols below.
- In addition, if possible, perform MRI of all additional measurable plexiform neurofibroma(s).

On study radiographic evaluation:

Unless clinically indicated otherwise obtain MRI of the index lesions only as outlined in the MRI acquisition protocol below prior to cycles 4, 7, 10, and then after every 6 cycles while on study.

MRI protocols:

Depending on the location of the index lesions the Spine, Head/Neck or Trunk/Extremities protocols outlined on the following pages will be used.

The measurement of very irregular or infiltrative neurofibromas will present major challenges, and in some cases, it may be difficult to precisely define tumor margins. If necessary, participating institutions may modify the MRI sequences to optimize differentiation of tumor and surrounding tissue. Modifications should be documented in the MRI protocols, and the same imaging protocol, and, if possible, the same MRI scanner, should be used for all subsequent MRI studies.

Every attempt should be made to image the entire progressive plexiform neurofibroma(s).

A written protocol for scanning each patient has to be established at the time of study entry to allow for reproducibility of follow-up studies.

All MRI studies requested per protocol will be submitted to the NCI POB within 2 weeks of acquisition for volume analysis. At the same time, a copy of the MRI protocol used to obtain the MRI study will be sent to the NCI POB, or faxed to [name] or [name] [contact]).

MRI Protocol- Spine

PATIENT ID NUMBER: _____

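### The any-one-lesion progression rule ties a child's event rate to the number of index lesions, and 5.4.2 commits neither the primary log-rank nor its back-up adjustment to account for that number

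*Combined protocol and SAP*

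**What the plan says.** Section 3.1.3, repeated in substance in 5.2, counts a child as progressed once there is a 20% or greater volume increase "of at least one of the index plexiform neurofibroma(s) compared to the pretreatment volume measured prior to the start of treatment". The index lesions are the plexiform neurofibromas that are progressing at entry. Section 2.2.5 caps them: if more than three are progressing, "the three most clinically relevant plexiform neurofibromas will be followed by 3-D MRI analysis". Appendix 4 gives the same maximum. A child therefore contributes one, two or three lesions to the endpoint.

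Section 5.4.2 compares 36 pirfenidone patients with the 30 patients of the initial placebo phase of the R115777 trial: "A Kaplan-Meier analysis using a log-rank test is the primary method of analysis to compare the two arms". It names no stratification factor or covariate. The sample size assumes that prognostic factors are distributed identically in the two trials.

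The same section accepts that patient differences could explain a result. It promises a comparison of patient characteristics between the arms. If an important prognostic factor differs at two-sided p<0.10, a Cox model is permitted but not required. No factors are listed, so index-lesion count is neither included nor excluded. The documents give no lesion counts for either arm.

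**The concern.** A child followed on three lesions has three chances to meet the threshold, and a child followed on one lesion has one. If lesions progress independently, the child's hazard is proportional to the count. The definition of the endpoint produces this, whether or not multiple lesions also mark worse disease.

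Randomisation would balance the count on average, but this comparison is not randomised. If pirfenidone children had fewer index lesions than the placebo children, an unadjusted one-sided test would reject too often with no drug effect. If they had more, a real effect could be hidden. The primary test has no term for the count, and the fallback depends on someone choosing to screen it, on the screen reaching p<0.10, and on the optional model then being fitted.

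**Working it through.** **1. The plan's own power figure.** Inputs from 5.4.2: 30 controls, "with 50% of the 30 patients on the previous trial having progressed, at a median of 6 months"; 36 new patients; "a doubling of the median time to progression, from 6 to 12 months"; one-sided 5%; accrual of 2.5-3 per month (12 to 14.4 months); analysis about 12 months after the last entry.

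Power = Φ( ln 2 / √(1/d1 + 1/d2) − 1.645 ), where d1 and d2 are control and pirfenidone events.

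- With exponential times and 12 months' accrual: d2 = 36 × [1 − (0.50 − 0.25)/0.693] = 23.0.
- If the 15 remaining controls stay under follow-up for 24 months: d1 = 15 + 15 × (1 − 0.0625) = 29.1.
- Power = Φ(0.693/0.279 − 1.645) = 0.799. With 14.4 months' accrual it is 0.807.

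The stated 80% reproduces on that follow-up assumption. The formula has no term for lesion count.

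**2. Effect of the count on a child's event rate.** If each lesion has hazard λ and lesions are independent, a child with k lesions has survival exp(−kλt), so hazard kλ. More generally, take the hazard as proportional to k^g, with g = 1 for independence and g = 0 when lesions progress together.

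The counts below are assumed:

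- Per-lesion median 9 months: λ = 0.693/9 = 0.0770 per month.
- Control: 18, 9 and 3 children with 1, 2 and 3 lesions; mean 45/30 = 1.50.
- Pirfenidone: 29, 5 and 2 children; mean 45/36 = 1.25.

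Let x = exp(−λt) and set arm survival to 0.5:

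- Control: 0.600x + 0.300x² + 0.100x³ = 0.5 gives x = 0.610, t = 6.4 months.
- Pirfenidone: 0.806x + 0.139x² + 0.056x³ = 0.5 gives x = 0.556, t = 7.6 months.

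The medians differ by about 1.2 months with no drug effect.

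**3. Type I error of the one-sided 5% log-rank, no drug effect.** Simulation settings: 30 against 36 patients, exponential lesion times with a shared gamma frailty, follow-up uniform over 6-24 months (control) and 12-25 months (pirfenidone). Mean counts and correlation are assumed.

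| Mean count, control v pirfenidone | tau 0 | tau 0.3 | tau 0.6 |
|---|---|---|---|
| Equal | 5-6% | 5-6% | 5-6% |
| 1.50 v 1.25 | 14% | 10% | 7-8% |
| 1.8 v 1.2 | 31% | 20% | 12% |

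Stratifying by 1 against 2-3 lesions gives about 4.5-6% in every case.

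A second model, with hazard proportional to k^g and the protocol's scan schedule, agrees. For 1.4 v 1.2 the error is 0.114 (g = 1) and 0.071 (g = 0.5). For 1.6 v 1.2 it is 0.203, 0.119 and, at g = 0, 0.055. Stratified, it is 0.049-0.056 throughout.

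**4. The p<0.10 screen applied to lesion count.** For the split in step 2, Fisher's test on 12/30 against 7/36 with more than one lesion gives p = 0.101. With counts drawn at random from populations with means 1.5 and 1.25, the screen fires in about half of trials. It fires in about 39% at 1.4 v 1.2, 82% at 1.6 v 1.2 and 96% or more at 1.8 v 1.2. If a flag always leads to adjustment, type I error is about 5-7%.

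**5. Power at a halved hazard.**

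- Reverse imbalance, 1.2 v 1.5, independent lesions: 47% unstratified, 67% stratified.
- Balanced counts: 68% unstratified against 72% stratified (tau 0), and 45% against 46% (tau 0.3).

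These compare the two tests within the simulation. Its follow-up differs from step 1, so they do not re-estimate the planned 80%.

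**The case against.** The strongest reply is that 5.4.2 already has a safeguard. A comparison of patient characteristics is promised, the baseline number of progressing lesions is such a characteristic, and nothing excludes it. Large imbalances would nearly always be flagged, and with adjustment the error falls to 5-7%. This stands, so the 14% and 31% figures must not be read as the error of the whole planned procedure. They apply if the count is not screened or the flag is not acted on. What survives is that the plan promises neither step and that moderate imbalances are missed about half the time. Whether the split in step 2 is flagged even depends on the test, which is not specified: Fisher gives 0.101, a rank test 0.077.

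A reader might also infer that the arms do differ in lesion count, or that the design favours pirfenidone. The documents support neither. They state identical eligibility, institutions and endpoint assessment, and with equal counts the unstratified test holds its level. Eligibility does not fix how many lesions are progressing, however, so balance is assumed rather than secured.

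Independence is the extreme case. Section 5.4.1 ties growth to childhood, with a plateau by the end of puberty. That is a shared driver within a child and would raise the correlation and shrink the effect.

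Lesion count can fairly be called one more prognostic factor. It differs in that the endpoint definition itself makes it act on the event rate, so it can be named in advance without outside evidence.

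Finally, section 1.2.10 reports enrolment complete and nine patients still on study in an open-label trial. Replacing the primary test at that stage needs justification, and the fix allows for this.

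**Conclusion.** The point holds as a gap in pre-specification. The event rate depends on index-lesion count unless lesions within a child progress together, the primary log-rank ignores the count, and the safeguard neither names it nor obliges adjustment.

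The size is conditional. At assumed means of 1.5 against 1.25, type I error is about 14% with independent lesions and 7-8% at tau 0.6. It is about 5-7% if the screen is applied to the count and always acted on, and nominal if counts are equal or lesions are fully correlated. The reverse imbalance costs power. The count distributions and the within-child correlation are assumptions, since neither is in the documents.

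The stronger conclusion, that a lesion-count difference will appear as a drug effect, is not supported. No imbalance is shown and its direction is unknown. In the second model the spurious pirfenidone medians are 6.9 to 8.8 months against a 6-month control for assumed means of 1.4, 1.6 and 1.8 against 1.2, all well short of the 12-month target.

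**What to change.** In 5.4.2, before the comparison is run, pre-specify a log-rank stratified by the number of index lesions at baseline (1 against 2-3), not conditional on a p<0.10 screen. Tabulate the count by arm, including each R115777 placebo child, and report the stratified and unstratified results together. If the sponsor keeps the unstratified test as primary because enrolment is complete, state in advance that a positive claim requires the stratified result to agree.

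The cost is one baseline count per control child and some analysis work. The pirfenidone counts are already known, because the coordinating branch measures the index lesions centrally. The sample size is unchanged, and the simulation shows no material loss of power when counts are balanced.
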